7.2 Secondary Endpoints

7.2.1 - Postoperative complications

- Hospital stay
- ICU admissions
- Postoperative bleeding
- Infection
- Anastomotic leak
- Respiratory complications
- Cardiac complications
- DVT/VTE
- Recovery of bowel function

- Time to ambulation
- Epidural complications

7.2.2 - Quality of Recovery/Patient Satisfaction

- Several short (5-10 minute), simple survey instruments will be utilized in this study to assess patient-centered perioperative pain control, and overall recovery, satisfaction. Although all of these survey instruments have been validated in other studies, none have been applied in the evaluation of patients undergoing liver and/or pancreatic surgery. The use of multiple instruments with some overlap in measures allows for redundancy in assessments and the determination of the accuracy of patient reporting. Such data will assist in comparing the efficacy of these various instruments in capturing the “true” quality of recovery in this subset of patients. Any variations and discrepancies in the reported redundant measures will assist in the formulation of a subsequent improved instrument for validation on a greater scale.

- The Health Outcomes Recovery Questionnaire (HORQ), a validated postoperative recovery instrument, will be administered daily for the first 5 postoperative days and includes questions regarding patient satisfaction, daily activities, and opioid-related symptoms (Appendix I).[64]
- The Postoperative Pain Survey (PPS), an outcome-oriented validated survey to assess quality improvement in postoperative pain management, will be administered daily for the first 5 postoperative days (Appendix J).[65]
- The Opioid-related Symptom Distress Scale (SDS), a validated and reliable measurement tool that measures twelve opioid-related symptoms, will be administered daily for the first 5 postoperative days (Appendix K).[66]
- The Quality of Recovery Survey (QoR), a useful and validated summary measure of recovery after anesthesia and surgery, will be administered daily for the first 5 postoperative days (Appendix L).[67]

7.2.3 - Immunologic correlates

-Cytotoxicity assays will be performed to detect NK and NKT killing activity. These assays will be done by flow cytometry. These assays will be from optional blood collected as described in 5.2.2.

-Cytokine determination will be done by ELISA technique using commercially available kits for each cytokine. These

assays will be from optional blood collected as described in 5.2.2.

7.2.4 - Pain score at each time point

- Mean pain scores at various time points will be compared between groups (TEA vs. IVPCA). There will be 6 specific timepoints that will be used for secondary analysis as each timepoint will be an independent measure and may differ between groups dependent on duration from surgery as was found in previous studies: 1). mean pain scores compared between groups at 6 hrs postop; 2). mean pain scores compared between groups for subsequent 18hrs postop; 3). mean pain scores compared between groups over 24hrs on postop day #2; 4). mean pain scores compared between groups over 24hrs on postop day #3; 5). mean pain scores compared between groups over 24hrs on postop day #4; and 6). mean pain scores compared between groups over 24hrs on postop day #5.

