6.5 Postoperative Pain Assessment (Both TEA and IVPCA Groups)

6.5.1 - Pain scores will be assessed in both groups with a Numeric/Visual Pain Scale (0-10) at various time points in the clinical record per current inpatient policies (Appendix F). Beginning in the PACU after surgery, pain will be assessed by nursing staff approximately every hour per current practice until disposition to inpatient care units. In the overnight recovery suite and general floor pain will be assessed by nursing staff approximately every 4 hours per current practice. In the SICU pain will be assessed by nursing staff approximately every hour per current practice. The pain assessments that are being used for analysis are average pain scores within first 6hrs postop, the next 18hrs, and each 24hr period thereafter. The pain scores for each 24 hour period after this will be averaged (as many as are collected). Pain will re-assessed by nursing staff approximately 1 hour after every analgesic intervention per current practice on all nursing floors. All dosing alterations, changes, and total narcotic/analgesic use will be documented in the clinical record per current practice.

6.5.2 - The Acute Pain Service team/nurse will assess all patients in both groups (TEA and IVPKA). Therapeutic analgesic interventions in the TEA group will be per discretion of the Acute Pain Service per current practice. Therapeutic interventions in the IVPKA group will be per discretion of the primary surgical team per current practice and the primary surgical team will be blinded to the Acute Pain Service assessment of patients in IVPKA group.

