7.1 Primary Endpoints

7.1.1 - Pain scores (Numeric/Visual Pain Scale)

Pain score AUC within the first 48 hours will be used as the primary endpoint. The AUC for each patient will be computed using the trapezoidal method using the pain score versus time curve. The mean AUC pain scores within the first 48 hours will be compared between TEA and IVPKA groups for the primary analysis.

7.1.2 - Quality of Life

- Patients will complete a validated SF-8, Acute Recall QOL survey (preoperatively and then at approximately 24hrs after surgery) (Appendix G)
- Patients will complete a validated SF-36v2, Acute Recall QOL survey (preoperatively and then prior to discharge or at approximately 1 week after surgery – whichever is first) (Appendix H).

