8.0 Statistical Considerations

8.1 Methodology

- This is a two-arm randomized non-blinded study whose primary objectives are to compare postoperative pain scores and quality of life (QOL) scores in patients undergoing liver and/or pancreatic resection between those receiving TEA versus IVPCA. Eligible patients will be randomized in a 3:1 allocation ratio to the treatment group of TEA or IVPCA group (to represent our current institutional practice as well as to allow a more accurate determination of overall TEA failures and complications). Randomization will be stratified by the resection type (liver or pancreatic - 1:1). The randomization will be conducted by the CORE prior to surgery and after consent and registration. Pain will be assessed using a numeric/visual pain score at various timepoints. The pain scores will be averaged for each patient and be compared between TEA and IVPCA groups at specific time points as follows: pain scores for the first 6 hours after surgery, pain scores for the next 18hrs after surgery, pain scores for each subsequent 24hr period after surgery until postoperative day #5 or epidural removed, whichever occurs first. QOL will be assessed pre- and postoperatively using SF-8 and SF-36v2. These validated instruments will score 8 domains that will be reduced to two summary measures scales, Physical Component Summary (PCS) and the Mental Health Component Summary (MCS). Scoring will be performed utilizing proprietary certified scoring software from the vendor. QOL scores will be calculated and compared between the two groups of patients.
- Categorical data will be tabulated with frequency and percentages, and continuous variables will be summarized using descriptive statistics mean, standard deviation, median and range. The primary

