endpoint for pain scores is mean pain scores within the first 48 hours, computed as the AUC the pain score vs. time curve for each individual. In case there is missing data, we will compute the AUC while using last value carried forward to fill in the missing data. For primary analysis, 2-sample t-tests or Wilcoxon rank sum test will be used to compare mean pain scores within 48 hours post operation between TEA and IVPCA arms. The same methods will also be applied to compare mean pain scores at each time point between TEA and IVPCA. Linear mixed models including treatment, evaluation time, and interaction of treatment and evaluation time will be fit to determine the treatment effect on pain scale. Each pain score in PPS form will be analyzed for the primary analysis. Chi-square test or Fisher's exact test will be used to compare the binary outcomes between the two arms, which are related to effects of pain on patients' movement or mood, such as pain's influence on mobility or movement, cough or breath deeply, sleep and mood. Generalized estimating equation (GEE) regression models will be fit to estimate the treatment effects on the listed binary outcomes. Chi-square test will be used to compare the categorical items of QOL pre and post surgery between the two treatment arms, the same method will also be used to compare the changes pre-postoperative in items of QOL between the two arms as well.

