8.2 Sample Size

- A total of 200 liver and pancreatic resection patients will be enrolled in order to achieve 140 evaluable patients. As these surgical procedures are for resection of malignancy, a proportion of patients will be identified with unresectable or metastatic disease at the time of planned resection either during initial laparoscopy or after open exploration. Those patients deemed unresectable at laparoscopy will not undergo open exploration, and thus, will be inevaluable for postoperative pain due to differences in incision type. Furthermore those patients that do undergo an open exploration but are deemed unresectable due to local or metastatic disease found intraoperatively will have markedly different prognoses compared to those that have a successful resection, which may bias their response to pain and quality of recovery and bias the questionnaire responses. Based on previous work at our and other institutions, it is expected that up to 30% of patients will not be evaluable due to various reasons, including ineligibility, patient withdrawal from the study, unresectable disease, and failure to complete or inaccurate completion of questionnaires. Based on historical information, if the difference in mean pain score between the two evaluable treatment groups of patients is 1 and the common standard deviation is 1.5, with a total of 140 evaluable patients (105 in TEA group and 35 in IVPCA group), the study will yield a 92% power to detect the difference, using a two-sample t-test at a two-sided significance level of 0.05. Furthermore, the study will have a 99% power to detect a difference of 10 in QOL score with a corresponding standard deviation of 9 using a two-sided Student's t-test with a type I error of 0.05. All statistical analyses will be performed with an intent to

treat methodology, including those patients who cross over between treatment groups.

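### The day 4 and day 5 pain tests compare only patients who still have inpatient scores, a group formed after randomisation, and no rule covers those already discharged

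*Combined protocol and SAP*

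**What the plan says.** Section 7.2.4 names six time-point comparisons of mean pain. The last two are postoperative days 4 and 5, the final one being "mean pain scores compared between groups over 24hrs on postop day #5".

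Section 6.5.1 gives the source. Pain is scored "at various time points in the clinical record per current inpatient policies", by nurses in the PACU, the SICU, the overnight suite or the ward. For the ward it says: "In the overnight recovery suite and general floor pain will be assessed by nursing staff approximately every 4 hours per current practice". Daily values are formed as follows: "The pain scores for each 24 hour period after this will be averaged (as many as are collected". No minimum number of scores is set, and no collection of this scale after discharge is described.

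Section 8.1 names a two-sample t-test or Wilcoxon test for the 48-hour primary comparison and adds: "The same methods will also be applied to compare mean pain scores at each time point between TEA and IVPCA". Last value carried forward is stated for the AUC only. A linear mixed model with treatment, time and their interaction is also planned, but it is not designated as the source of the day 4 and day 5 contrasts.

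Section 8.2 states: "All statistical analyses will be performed with an intent to" treat approach, crossovers included. Section 7.1.2 foresees some discharges within about a week, because the SF-36v2 is due "prior to discharge or at approximately 1 week after surgery – whichever is first". Hospital stay is itself a secondary endpoint (7.2.1).

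Section 8.1 also ends the averaging early: "pain scores for each subsequent 24hr period after surgery until postoperative day #5 or epidural removed, whichever occurs first". Section 7.2.4 has no such cut-off.

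**The concern.** A patient who has gone home still has pain, but it is not charted. That patient has no day 5 value and drops out of the two-sample test without any rule saying so. The groups compared are then no longer the randomised arms. They are the patients who remain, and remaining in hospital is an outcome that treatment may influence.

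If patients with less pain leave earlier, the mean of those who remain is too high. If more of them leave from the TEA arm, the TEA mean is raised more and the contrast moves against TEA. Sections 2.5 and 2.8 express the belief that TEA shortens stay, so the plan's own expectation points this way. At stake is how late pain control is reported, on two of the six secondary time points.

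The cut-off at epidural removal is a second and separate selection. Apart from crossovers under 4.1.2, only TEA patients have an epidural to remove. Section 4.2.1 ties removal to tolerating diet or tube feeds and moving to oral or enteral analgesics, so it would usually come before discharge. Deleting the cut-off would still leave the selection by discharge.

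**Working it through.** **1. The plan's own figure.** From 8.2: 105 v 35 evaluable patients, difference 1, SD 1.5, two-sided 0.05. Standard error = 1.5 × √(1/105 + 1/35) = 0.293. Ratio = 1/0.293 = 3.416. Power is 92.4% by the noncentral t (138 df) and 92.7% by the normal approximation, so the stated 92% reproduces. The documents give no figure specific to day 4 or day 5; 0.29 serves below as a yardstick.

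**2. One record, read literally.** Day 4 is hours 72 to 96 and day 5 is hours 96 to 120. A ward patient present throughout has about 24/4 = 6 scores in each window. A patient discharged at hour 80 has about (80 − 72)/4 = 2 scores for day 4 and none for day 5.

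**3. Closed-form size.** Inputs: SD 1.5 (8.2); share discharged p (assumed); correlation ρ between lower pain and earlier discharge (assumed). Under a normal selection model, the mean of those remaining rises by ρ × 1.5 × φ(z_p)/(1 − p).

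- p = 0.20: 0.280/0.80 = 0.350. p = 0.10: 0.1755/0.90 = 0.195. The difference is 0.155. Bias (TEA minus IVPCA) = 0.155 × 1.5 × ρ = +0.05 at ρ = 0.2 and +0.12 at ρ = 0.5.
- p = 0.30 v 0.10: 0.497 − 0.195 = 0.302. Bias = +0.09 at ρ = 0.2 and +0.23 at ρ = 0.5.
- Equal p, or ρ = 0: the bias in the contrast is 0.

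**4. Simulation using the protocol's windows.** Six windows, SD 1.5, assumed within-patient correlation 0.6, no true day 5 difference. Discharge before day 5 is logistic in the day 4 score, with the odds of discharge falling by a factor of 1.65 or 2.7 per point of pain. The comparison uses patients with a day 5 value.

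| Discharged, TEA v IVPCA (assumed) | Bias, points | Bias / 0.29 |
|---|---|---|
| 5% v 2% | about 0.03 or less | about 0.1 or less |
| 20% v 10% | +0.06 to +0.09 | 0.2 to 0.3 |
| 40% v 20% | +0.12 to +0.18 | 0.4 to 0.6 |
| 50% v 25% | +0.15 to +0.23 | 0.5 to 0.8 |
| 30% v 30% | about 0 | 0 |

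In the 30% v 30% case each arm mean is still about 0.18 to 0.30 points too high.

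**5. What the mixed model would do.** In the simulation of step 4, an estimate that uses the earlier windows left a bias of 0.01 or less. That follows from the set-up, because discharge was made to depend only on recorded pain. In a second simulation (ρ = 0.5, conditioning on the preceding day only), discharge depended on the unrecorded day 5 pain. A bias of 0.12 at 20% v 10% then fell only to 0.08, and 0.23 at 30% v 10% fell only to 0.15, so about two thirds remained (0.08/0.12 = 0.67; 0.15/0.23 = 0.65). Using more earlier windows reduces this remainder but does not remove it.

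**The case against.** The strongest reply is that bias is not shown. It needs material discharge by day 4 or 5, shares that differ by arm, and a link with pain, and the documents quantify none of these. The procedure-specific evidence in 2.7 points away from a difference: the retrospective pancreatic series found no difference in stay, and the retrospective liver series found no shorter stay with epidurals. Blood sampling and daily surveys run to day 5, and catheters may stay up to 7 days, which suggests that many patients are still inpatients then. Length of stay may also be driven by bowel recovery or complications rather than pain. All of this stands. A reader might infer that the late tests are known to be biased, or that a late benefit would be reversed. The documents support neither. Even +0.23 could not reverse a true 1-point benefit; reversal would need a late effect already near zero.

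A second reply is that the cut-off at epidural removal usually acts first, so under 8.1 the late TEA means describe patients with a catheter still in place, not simply patients still in hospital. That is correct, and it is why the two sections must be reconciled first.

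A third reply is that the mixed model and the daily Postoperative Pain Survey already cover the gap. The model is planned, but the two-sample tests are what 8.1 assigns to each time point. The survey runs through day 5, but where it is completed is not stated, and it is a separate instrument from the scale in 7.2.4.

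What survives is narrower: the comparison as specified is not between the randomised arms, and no rule deals with patients who have left.

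**Conclusion.** The concern holds as a defect of specification and method for the secondary day 4 and day 5 comparisons. The named tests would use a group selected after randomisation, contrary to 8.2. The direction, against TEA, is conditional on pain-related discharge that is more frequent with TEA. Sections 2.5 and 2.8 expect shorter stay with TEA; the series in 2.7 did not find it.

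The size is an assumption, not a finding. It is well under one standard error in every scenario tabulated and zero for the contrast at equal discharge shares, though the reported arm means are then inflated. The 48-hour AUC and its 92% power are untouched. It would also go too far to infer that the mixed model eliminates the problem: it does so only if discharge depends on pain already recorded.

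**What to change.** - Reconcile the epidural-removal cut-off in 8.1 with 7.2.4, so that the analysis window is defined identically in both arms.
- In 7.2.4 and 8.1, take the day 4 and day 5 treatment contrasts from the planned linear mixed model. Fit it to all available windows of all patients in the intent-to-treat analysis, with time as a category and unstructured covariance.
- State the missing-at-random assumption: discharge depends on pain already recorded.
- Add a simple missing-not-at-random sensitivity analysis that shifts the unobserved late values by a stated delta, varied by arm.
- Report the number contributing per arm and window, and label raw late means as describing patients still in hospital.

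The cost is SAP wording and one extra sensitivity analysis; no new data are needed. The downside is that the late contrasts rest on a modelling assumption and the raw late means become descriptive.

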8.0 Statistical Considerations

8.1 Methodology

- This is a two-arm randomized non-blinded study whose primary objectives are to compare postoperative pain scores and quality of life (QOL) scores in patients undergoing liver and/or pancreatic resection between those receiving TEA versus IVPCA. Eligible patients will be randomized in a 3:1 allocation ratio to the treatment group of TEA or IVPCA group (to represent our current institutional practice as well as to allow a more accurate determination of overall TEA failures and complications). Randomization will be stratified by the resection type (liver or pancreatic - 1:1). The randomization will be conducted by the CORE prior to surgery and after consent and registration. Pain will be assessed using a numeric/visual pain score at various timepoints. The pain scores will be averaged for each patient and be compared between TEA and IVPCA groups at specific time points as follows: pain scores for the first 6 hours after surgery, pain scores for the next 18hrs after surgery, pain scores for each subsequent 24hr period after surgery until postoperative day #5 or epidural removed, whichever occurs first. QOL will be assessed pre- and postoperatively using SF-8 and SF-36v2. These validated instruments will score 8 domains that will be reduced to two summary measures scales, Physical Component Summary (PCS) and the Mental Health Component Summary (MCS). Scoring will be performed utilizing proprietary certified scoring software from the vendor. QOL scores will be calculated and compared between the two groups of patients.
- Categorical data will be tabulated with frequency and percentages, and continuous variables will be summarized using descriptive statistics mean, standard deviation, median and range. The primary

endpoint for pain scores is mean pain scores within the first 48 hours, computed as the AUC the pain score vs. time curve for each individual. In case there is missing data, we will compute the AUC while using last value carried forward to fill in the missing data. For primary analysis, 2-sample t-tests or Wilcoxon rank sum test will be used to compare mean pain scores within 48 hours post operation between TEA and IVPCA arms. The same methods will also be applied to compare mean pain scores at each time point between TEA and IVPCA. Linear mixed models including treatment, evaluation time, and interaction of treatment and evaluation time will be fit to determine the treatment effect on pain scale. Each pain score in PPS form will be analyzed for the primary analysis. Chi-square test or Fisher's exact test will be used to compare the binary outcomes between the two arms, which are related to effects of pain on patients' movement or mood, such as pain's influence on mobility or movement, cough or breath deeply, sleep and mood. Generalized estimating equation (GEE) regression models will be fit to estimate the treatment effects on the listed binary outcomes. Chi-square test will be used to compare the categorical items of QOL pre and post surgery between the two treatment arms, the same method will also be used to compare the changes pre-postoperative in items of QOL between the two arms as well.

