4.1 IVPCA

4.1.1 - Immediately following surgery, the OR Anesthesia team will titrate intravenous narcotics in the PACU for pain down to an acceptable level prior to initiating IVPCA. All patients assigned to IVPCA group will be started on intravenous patient-controlled analgesia protocol according to current institutional policy following surgical procedures. All patients will be given hydromorphone as the opioid of choice per current practice, unless there are contraindications. Fentanyl or Morphine will be secondary alternatives. Initial recommended starting doses are: no basal rate, 0.2mg every 10 minutes demand dosing, and a 0.5mg nursing bolus every 1 hour as needed for additional pain control (Appendix A). Adjunctive use oral, rectal, or intravenous non-narcotic analgesics (acetaminophen, non-steroidals, etc.) will be utilized at the discretion of the Primary Surgical Team.

4.1.2 - Patients whose IVPCA's are not functioning or not providing adequate analgesia will be considered for possible postoperative placement of TEA (coagulation studies permitting) as an alternative analgesic regimen (patient crossover).

4.1.3 - Further drug information can be found in the MDACC formulary and the FDA approved package inserts of the medications as they are all commercially available.

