4.2 TEA

4.2.1 - All patients assigned to TEA will have thoracic epidurals placed preoperatively in either the holding area or in the operating room according to current institutional protocol. Epidural catheters will be placed between the Thoracic 5th-Thoracic 10th interspinous levels using standard technique according to institutional practices. All epidural catheters will be tested for correct placement and level of block documented and secured as is currently practiced. The epidural will be initially dosed according to current practices with hydromorphone (10 mcg/kg for pts 65 yrs or younger and 5 mcg/kg for pts > 65yrs) after induction of anesthesia. Standard epidural solutions are: Hydromorphone (10 mcg/ml for pts 65yrs or younger and 5 mcg/ml for pts > 65yrs) and Bupivacaine (0.075%) at 10 ml/hr continuous infusion and a 3ml every 10 minutes demand dosing, and a 5ml every 3 hours clinician bolus as needed for additional pain control (Appendix B). Fentanyl with Bupivacaine

will be secondary alternatives. Adjunctive use of oral, rectal, or intravenous non-narcotic analgesics (acetaminophen, non-steriodals, etc.) will be utilized at the discretion of Acute Pain Service and/or Primary Surgical Team. Epidural catheters will remain in place a maximum of 7 days postoperatively. Epidural catheters will be removed once patients are successfully tolerating a full diet or tube feeds and are transitioned to oral/enteral analgesics. Indwelling urinary catheters will be removed after TEA removal per current policy.

4.2.2 - Patients whose TEA's are not functioning or not providing adequate analgesia will be considered for IVPCA as an alternative analgesic regimen (patient crossover).

4.2.3 - Further drug information can be found in the MDACC formulary and the FDA approved package inserts of the medications as they are all commercially available.

5. Treatment Plan – Perioperative Monitoring

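### Section 8.1 ends the charted daily pain means at epidural removal, a post-randomisation event almost confined to the TEA arm, while Sections 6.5.1, 7.2.4 and 8.2 imply no such cut-off (secondary endpoint only)

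*Combined protocol and SAP*

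**What the plan says.** Section 8.1 sets out how charted pain scores are averaged and compared between arms: the first 6 hours, the next 18 hours, then "pain scores for each subsequent 24hr period after surgery until postoperative day #5 or epidural removed, whichever occurs first". It applies a t-test or Wilcoxon test at each time point and also plans a mixed model with treatment, time and their interaction.

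Two other sections define the same periods without reference to the catheter. Section 6.5.1 says the "pain assessments that are being used for analysis are average pain scores within first 6hrs postop, the next 18hrs, and each 24hr period thereafter", and adds: "The pain scores for each 24 hour period after this will be averaged (as many as are collected". Section 7.2.4 lists six between-group comparisons, the last being "mean pain scores compared between groups over 24hrs on postop day #5".

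Section 8.2 states that all analyses follow intent to "treat methodology, including those patients who cross over between treatment groups".

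On removal itself, 4.2.1 says: "Epidural catheters will be removed once patients are successfully tolerating a full diet or tube feeds and are transitioned to oral/enteral analgesics". It also allows a catheter to stay for up to 7 days, so removal can fall before or after day 5. On failure, 4.2.2 says: "Patients whose TEA's are not functioning or not providing adequate analgesia will be considered for IVPCA as an alternative analgesic regimen". In the other direction, 4.1.2 allows an IVPCA patient with inadequate analgesia to be "considered for possible postoperative placement of TEA (coagulation studies permitting) as an alternative analgesic regimen (patient crossover".

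**The concern.** Catheter removal is decided after randomisation and depends on how the patient is recovering. It may also depend on TEA failure, although the documents do not say that the catheter comes out at crossover. Every TEA patient is assigned an epidural. An IVPCA patient has one only after crossover, and no parallel rule ends IVPCA data. A rule that stops counting scores at removal therefore selects patients in one arm on something that may be related to pain.

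Two things are at stake. The later-day comparisons of charted means would lose the protection of randomisation. And two analysts, one following 8.1 and the other following 6.5.1 and 7.2.4, could report different means for the same days from the same data. Section 7.2.4 justifies the separate time points by saying that the groups may differ according to time since surgery, so the later days are part of the purpose of this endpoint.

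**Working it through.** **1. The texts side by side**

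| Section | Periods | Stops at epidural removal? |
|---|---|---|
| 6.5.1 | 0-6 h, next 18 h, each later 24 h | No; averages whatever is collected |
| 7.2.4 | Six periods through day 5 | No |
| 8.1, time-point means | Same periods through day 5 | Yes |
| 7.1.1 and 8.1, primary AUC | 0-48 h | No |
| 7.2.2, PPS | Daily, days 1-5 | No |
| 8.2 | All analyses | Intent to treat, crossovers included |

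No passage reconciles 8.1 with the others or says how the cut-off applies to a patient who has no epidural.

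**2. Which time points are exposed**

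On its plain reading the clause keeps scores charted before removal, so a patient removed during a period still contributes to that period's mean. A TEA patient is absent from the day 2 mean (24-48 h) only if the catheter is out before 24 h. The exposure is therefore mainly days 3, 4 and 5.

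**3. The plan's own figure**

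Inputs from 8.2: difference 1, SD 1.5, 105 TEA and 35 IVPCA evaluable patients, two-sided 0.05.

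- Standard error = 1.5 × √(1/105 + 1/35) = 0.293.
- Non-centrality = 1/0.293 = 3.42, with 138 degrees of freedom.
- Power = 92.4%, matching the stated 92%.

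Losing TEA patients without any selection costs little: power is 91.6% with 94 vs 35 (10% lost) and 85.4% with 52 vs 35 (50% lost). The issue is selection, not power.

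**4. Illustration of the selection effect**

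Assumptions, none of them from the documents except the SD: a share p of TEA patients no longer contributes to a period; removal and that period's pain have absolute correlation r of 0.3 to 0.5; the SD of 1.5 given in 8.2 for the design also holds for a daily mean and for the retained patients; there is no true difference.

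Shift in the retained TEA mean = r × 1.5 × φ(z_p)/(1 − p), where φ is the normal density and z_p the p-quantile. Rejection comes from the noncentral t with 105 × (1 − p) TEA patients against 35.

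| p | φ(z_p)/(1−p) | TEA n | Shift, r = 0.3 to 0.5 | Null rejection (nominal 5%) |
|---|---|---|---|---|
| 5% | 0.109 | 100 | 0.05-0.08 | 5.3-5.9% |
| 10% | 0.195 | 94 | 0.09-0.15 | 6.0-7.8% |
| 25% | 0.424 | 79 | 0.19-0.32 | 9.5-18% |
| 50% | 0.798 | 52 | 0.36-0.60 | 19-44% |

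Example: p = 25%, r = 0.5 gives 0.5 × 1.5 × 0.424 = 0.318. The shift is upward if low-pain patients leave and downward if failures leave; the two can offset each other.

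**5. The mixed model**

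These figures do not carry over to a likelihood-based mixed model, which retains the earlier scores of removed patients. A simulation used assumed inputs: 105 vs 35, six periods, SD 1.5, exchangeable correlation 0.3, 0.5 or 0.7, no true difference, and removal from the third period on. Removal was logistic, with baseline 0.06 or 0.17 per period and slope −0.8 per SD of same-period pain, so that low-pain patients leave. About 26-57% of catheters were out by day 5. With scores up to removal kept, the observed day 5 means were biased by about 0.07-0.41 points and the mixed model by about 0.015 or less.

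**The case against.** The strongest reply is that this is a wording inconsistency in one secondary endpoint, and that the plan already contains much of the answer. The primary 48-hour AUC carries no removal cut-off, PPS pain scores run daily to day 5, and the intent-to-treat statement in 8.2 gives an analyst a documented basis for keeping scores after removal. No figure in the documents shows a material effect: the removal shares and correlations above are assumptions, and with few catheters out the effect is negligible.

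Most of this stands and limits the point. It does not remove it. Intent to treat fixes the arm in which a patient is analysed; it does not clearly override a more specific sentence saying which scores are averaged. That sentence sits in the methodology section and governs a between-group comparison, so it cannot be read as a data-collection window only.

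A reader might infer more than the documents support:

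- *That the primary result is biased.* The AUC is defined without the clause, and nothing says that scores after removal are treated as missing.
- *That days 2 to 5 are equally exposed.* Under 4.2.1 planned removal needs a tolerated full diet or tube feeds and a change to oral or enteral analgesics. Nothing in the documents suggests that many patients reach this within 24 hours, so day 2 is marginal.
- *That the comparison is with every IVPCA patient.* A crossed-over IVPCA patient also has a catheter to remove; the contrast is with essentially the whole arm.
- *That the mixed model is materially biased too.* In the simulation, a clear mixed-model bias (0.05-0.23 points) appeared only when the whole removal period was discarded and removal depended on pain in that same period. The clause does not call for that deletion.

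**Conclusion.** The contradiction is real. Section 8.1 applies a post-randomisation, recovery-linked cut-off that falls almost only on TEA, while 6.5.1 and 7.2.4 define the same means without it and 8.2 calls for intent to treat. Followed as written, 8.1 makes the t-test or Wilcoxon comparisons of charted means on days 3 to 5, and marginally day 2, something other than the randomised comparison.

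The size and direction of any bias cannot be determined, because the documents give neither removal rates nor a link between removal and pain. A reader might infer that the rule favours TEA; the documents do not support a direction either way. On the assumed inputs the effect ranges from trivial (5% out) to material (25-50% out).

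The textual conflict is certain whatever the size. Severity is minor to should-fix, because only a secondary endpoint is affected.

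**What to change.** In 8.1, delete the words that end the daily averages at epidural removal, so that the periods run through postoperative day 5 in both arms. Alternatively, keep the cut-off only as a clearly labelled supplementary on-treatment analysis. State that all charted scores through day 5 are analysed by randomised arm regardless of epidural removal or crossover, consistent with 6.5.1, 7.2.4 and 8.2.

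This is a change of analysis wording. Section 6.5.1 already has nursing staff chart pain scores in both arms, so no new data are needed, and the sample size and stated power do not change. The small downside is that the later-day TEA means will include pain after the catheter is out. A reader who wants pain while the epidural is running can take that from the supplementary analysis.
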